## 1.4 Rationale for the Study and Purpose

Our phase I trials (see section 1.3) showed that NR holds promise as a potential neuroprotective, disease-modifying therapy for PD, and that its effects are likely to be dose-dependent. Encouraged by these findings, this project aims to determine the optimal biological dose of NR in PD and to further explore its neuroprotective potential. The outcomes of this project will take us several steps closer to developing NR into a PD-drug, so that we may harness its full therapeutic potential and maximize its clinical benefit and impact. Specifically, the following knowledge gaps (KG) will be addressed by the N-DOSE study:

**KG1 – Determine the Optimal Biological Dose (OBD) of NR in PD.** We define the OBD of NR as the dose required to achieve maximal cerebral NAD increase (measured by P-MRS or CSF metabolomics), or maximal expression increase in the NRRP (measured by FDG-PET), or maximal proportion of MRS-responders, in the absence of unacceptable toxicity.

While our trials show that the treatment responses to NR in PD are clearly dose-dependent, the OBD of NR in PD remains undetermined. Based on the results of NR-SAFE, it is likely that improved biological and clinical responses can be achieved by escalating the dose. Moreover, the NR OBD may not be universal. NADPARK showed that the NR-mediated increase in cerebral NAD-levels, and accompanying metabolic and clinical response, are not universal and vary across individuals. The fact that all NR-recipients showed a robust metabolic response in blood, muscle and CSF, suggests that the variable cerebral NAD response may reflect interindividual variability in cerebral NAD metabolism (i.e., variation in the rate of NAD-synthesis or consumption). It is likely that such differences can be modulated by varying the substrate concentration (i.e., the intake dose of NR). This question is critical to address, so that NR-therapy can be correctly dosed and tailored to individual patients to achieve an optimal neurometabolic response.

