## 10 STATISTICAL METHODS AND DATA ANALYSIS

### 10.1 Determination of Sample Size

Our primary null hypothesis ( $H_0$ ) is that the NR-induced increases in cerebral NAD levels (measured by 31P-MRS) are not dose-responsive. The alternative hypothesis ( $H_A$ ) is that this measure is dose responsive. In the NADPARK study, all three measures showed a highly significant increase in the group receiving 1000 mg NR ( $n = 15$ ) compared to the placebo group ( $n = 15$ ). In the NADPARK study, treatment with 1000mg of NR led to an increase in cerebral NAD-levels by a factor of 1.27 from baseline in the treatment group, whereas the change in the placebo group was negligible at -0.43%. Under the  $H_A$ , we assume that cerebral NAD levels will increase in a linear fashion in the 2000 mg NR and 3000 mg NR groups, respectively. Based on these assumptions and given a type I error rate of 5% ( $\alpha = 0.05$ ) and a type II error rate of 10% ( $\beta = 0.1$ , power = 90%), we estimated that a sample size of 30 individuals will be required in the dose escalation group. Accounting for drop-out and statistical safety margin, we estimate that the study requires 40 subjects in this group.

For the secondary and exploratory outcomes, we assume that the metabolomic, transcriptomic and inflammatory cytokine analyses will have sufficient power, since they produced very large effect sizes and highly significant results in the NADPARK study with 15 individuals per group. Since no pilot data exists for the proteomic and epigenomic analyses, these will be exploratory in nature. However, in our previous experience, a sample size of 20 per group should be sufficient to detect treatment-induced differences of biological relevance.

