## N-DOSE Protocol v3.1

The Safety Analysis Set (SAS) will include all patients having received at least one study treatment infusion after randomisation.

The Per Protocol Analysis Set (PPS) will include all randomized patients meeting the study eligibility criteria and with no major protocol deviations affecting the treatment efficacy.

The following are pre-defined major protocol deviations regarded to affect the efficacy of the intervention:

- Entering the trial when the eligibility criteria should have prevented trial entry.
- Discontinuation of intervention prior to  $84 \pm 7$  days.
- Major change in concomitant anti-Parkinson medication.
- Received or used other intervention than allocated.
- Adherence to allocated treatment below 85%.
- Visit date interval larger than  $28 \pm 7$  days between individual visits (i.e.: V1 and V2, V2 and V3 and V3 and V4)\*.
- Visit date interval larger than  $84 \pm 7$  days from V1 to V4\*.
- Not fasting before neuroimaging.

\*Due to updated findings from a pharmacokinetic study (ClinicalTrials.gov, NCT: NCT05698771, in revision) that NAD levels increase and reach a plateau within 1-2 weeks of NR treatment both in healthy individuals and persons with Parkinson's disease. A 3 week period should therefore be sufficient to assess the effects of increasing NR dosage.

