## 10.4 Planned analyses

All statistical analyses will take place after the completion of the study. All randomized patients will be included in the primary analyses and sensitivity analyses will be carried out comparing results from the ITT, SAS and PPS data sets. In the case of missing assessments, the subject will be included if possible.

The **primary analysis** of the primary endpoint will be performed using analysis of covariance (ANCOVA) between the dose stable (DS-group) and dose escalation group (DS-group), i.e. the regression of NAD levels measured by  $^{31}\text{P}$ -MRS at week 12 depending on randomization group and adjusted for  $^{31}\text{P}$ -MRS at baseline. No additional adjustments/covariates will be used. As this is the single primary outcome, alpha will be set at 0.05. No correction for multiple testing will be performed.

The **secondary analysis** of the primary endpoint will be the comparison of change over time from baseline to week 4, week 8 and week 12, between the DE-group and the DS-group. This will be assessed using a linear mixed model (LME), i.e. NAD ( $^{31}\text{P}$ -MRS) at weeks 4,8 and 12 depending on randomization group, time and their interaction adjusted for random individual intercept.

The **primary analysis** of the secondary endpoint will be performed using ANCOVA between the dose stable (DS-group) and dose escalation group (DS-group), i.e. the regression of NAD or NAD metabolite levels measured by HPLC-MS at week 12 depending on randomization group and adjusted for NAD or NAD metabolite at baseline. No additional adjustments/covariates will be used.

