#### 1.3.2 Secondary Objectives

The secondary objectives of this study are to:

- Assess the dose-response relationship between NR dose (1000 mg, 2000 mg, 3000 mg per day) and changes in cerebral NAD levels from baseline to weeks 4, 8 and 12.

- Compare the effectiveness of orally administered nicotinamide riboside (NR) 1500 mg twice per day versus 500 mg twice per day in augmenting the NAD-metabolome in the central nervous system (CNS) at week 12.

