### 5.1.7 Secondary Analyses of the Primary Endpoint

The *secondary analyses* of the *primary endpoint* will be:

1. Analysis of covariance (ANCOVA) between the dose stable (DS-group) and placebo group (PL-group), i.e. the regression of NAD levels measured by P-MRS at week 12 depending on randomization group and adjusted for P-MRS at baseline. No additional adjustments/covariates will be used. No correction for multiple testing will be performed.

The above-mentioned analysis will be performed in the same manner as the primary analysis for the primary endpoint.

2. Comparison of change over time from baseline to week 4, week 8 and week 12, between the DE-group, DS-group and the PL-group. This will be assessed using a linear mixed model (LME), i.e. NAD (P-MRS) at weeks 4, 8 and 12 depending on randomization group, time and their interaction adjusted for random individual intercept. The above-mentioned analysis will be performed using a linear mixed model (LME) comparing NAD level as a function of group with time and the interaction between group and time as independent variables. Individual subjects will be random effects.

The following formula will be used in R format:

```
NAD_level ~ Group + Visit + Group * Visit + (1 | Subject)
```

Visit will be treated as a numeric variable if there is no plateau effect. If there is a plateau effect in the data, visit will be treated as a factor.

The primary effect estimate will be the B-coefficient with confidence intervals and Cohen's d. Cohen's d will be calculated as the difference in the means between two groups and divided by the pooled standard deviation.

The dose stable group will be set as the reference to which the dose escalation and placebo groups will be compared.

No additional covariates will be included in the LME model.

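### SAP 5.1.7 lets an undefined plateau judgement decide how visit is coded in the 31P-MRS mixed model; if visit is numeric, the slope cannot show whether 3000 mg adds to 2000 mg, and no such contrast is named under either coding

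*SAP*

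**What the plan says.** The first secondary objective in SAP 1.3.2 is to "Assess the dose-response relationship between NR dose (1000 mg, 2000 mg, 3000 mg per day) and changes in cerebral NAD levels". Protocol 1.4 gives the wider purpose: "this project aims to determine the optimal biological dose of NR in PD". DE patients take 1000, 2000 and 3000 mg in months one, two and three, so week 8 is their only scan on 2000 mg. DS patients stay on 1000 mg.

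Both planned 31P-MRS ANCOVAs use baseline and week 12 only. The week-8 scan enters inference through one model, the linear mixed model in SAP 5.1.7, with group, visit, their interaction and a random intercept, and DS as reference. Its coding rule has two branches: "Visit will be treated as a numeric variable if there is no plateau effect", and "If there is a plateau effect in the data, visit will be treated as a factor". The SAP does not say how a plateau is to be judged, in which group, or when.

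The outcome visits are also unclear. Protocol 10.4 models NAD "at weeks 4,8 and 12 depending on randomization group, time and their interaction adjusted for random individual intercept", and SAP 5.1.7 says the same. Yet both call the analysis change over time from baseline, and the SAP adds: "No additional covariates will be included in the LME model". Baseline could then enter only as a fourth outcome visit.

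**The concern.** A group-by-visit slope with numeric visit forces the DE-DS step from week 4 to week 8 (2000 v 1000 mg) to equal the step from week 8 to week 12 (3000 v 2000 mg). That matches the planning assumption in Protocol 10.1, "we assume that cerebral NAD levels will increase in a linear fashion", but it is an assumption that a dose-response analysis should be able to test. Whether the model can test it depends on a judgement made after seeing the data.

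The stake is the dose taken forward. A steeper DE slope rightly counts against no dose-response, but it looks much the same whether the gain is complete at 2000 mg or appears only at 3000 mg. SAP 4.4 and 5.3 carry the same methods, provisionally, to FDG-PET pattern expression and the clinical scales.

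**Working it through.** **Inputs.** Groups of 40 DE, 20 DS and 20 placebo (Protocol 3.1, SAP 1.2); DE dose by visit as above; two-sided 5% level (SAP 2.3.2). The plan gives no figure for this model to reproduce. The DE sample size of 30 in Protocol 10.1 and SAP 5.5 is not tied to it and comes with no SD. Effects are therefore in units of the residual (within-patient) SD, over an assumed range of 0.5 to 1.0.

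**1. Weight of each visit in the slope.** With a random intercept and complete data, the weight is (x − mean x)/Sxx, with x in visit steps.
- Weeks 4, 8, 12: x = −1, 0, 1; Sxx = 2; weights −0.5, 0, 0.5.
- Weeks 0, 4, 8, 12: x = −1.5, −0.5, 0.5, 1.5; Sxx = 5; weights −0.3, −0.1, 0.1, 0.3.

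The weights are the same at within-patient correlations of 0, 0.3, 0.5 and 0.8.

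**2. Expected DE-DS slope.** D is the gain of 3000 over 1000 mg.

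| Where the gain comes | DE-DS at weeks 4, 8, 12 | Three visits | Four visits | Factor coding, week 12 − week 8 |
|---|---|---|---|---|
| All at 2000 mg | 0, D, D | 0.5D | 0.1D + 0.3D = 0.40D | 0 |
| Half at each step | 0, D/2, D | 0.5D | 0.05D + 0.3D = 0.35D | D/2 |
| All at 3000 mg | 0, 0, D | 0.5D | 0.3D = 0.30D | D |

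As a check, the mixed model was fitted to one simulated data set in which only the DE week-8 values were raised, by 0, 0.5, 1 and 3 residual SD. The three-visit slope was 0.6465 in all four fits. The factor-coded week 12 minus week 8 contrast was 1.49, 0.99, 0.49 and −1.51.

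**3. How often the slope interval lies above zero when 2000 and 3000 mg are equal.** The group factor is √(1/40 + 1/20) = 0.274.
- Three visits: SE = √0.5 × 0.274 = 0.194. At D = 0.5, 0.25/0.194 = 1.29, so P(Z > 1.96 − 1.29) ≈ 25%. Simulation at D = 0.5, 0.75, 1.0: 25%, 47%, 71%.
- Four visits: SE = √0.2 × 0.274 = 0.122. At D = 0.5, 0.20/0.122 = 1.63, giving about 37%. Simulation: 37%, 68%, 90%.

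These rates precede any switch to factor coding. With visit always a factor, the 3000 v 2000 mg interval lies above zero in about 2.5%.

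**4. With the switch, three visits.** The rate is now the share of trials with either a positive slope under numeric coding or a positive 3000 v 2000 mg contrast after switching. The SAP gives no definition of a plateau, so five possible ones were tried over the same range of D.

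| Plateau declared if | Rate |
|---|---|
| DE week 12 not significantly above week 8 | 3–4% |
| Last DE step under half the previous one | 5–7% |
| DE week-12 mean not above week 8 | 17–40% |
| Significant curvature within DE | 19–25% |
| Significant group-by-visit curvature | 23–49% |

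**5. Precision of the 3000 v 2000 mg contrast.** Half-width = t(58) × 0.274 = 2.002 × 0.274 = 0.55 SD of the week 8–12 change, or 0.55 × √2 ≈ 0.78 residual SD. At 36 v 18 patients it is 0.58 SD of the change. Power is about 25%, 48% and 72% for true steps of 0.5, 0.75 and 1.0 residual SD.

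**The case against.** Four points against the concern carry weight.

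- **Numeric coding is one branch, not an unconditional default.** Equality of 2000 and 3000 mg is itself a plateau, which the SAP would send to factor coding. That is so if it is recognised, but step 4 shows how far recognition depends on the definition. Protocol 10.3 also speaks of a plateau in another sense, NAD levelling off within 1–2 weeks of treatment, so even a flat DS course might be taken as the trigger. The 3–49% range shows an unsettled rule; it does not size a bias.
- **A reader might infer that the 2000 mg scan never counts.** The documents do not support that. Zero weight needs weeks 4, 8 and 12 as the outcomes and complete data. With baseline as an outcome visit the weight is 0.1, and missing visits also break exact zero.
- **A reader might take the 25–71% and 37–90% as false-positive rates.** They are not. The null in SAP 2.3.1 is no dose-response, and in the simulated truth there is one, so these are correct rejections. They mislead only if the slope is read as 3000 over 2000 mg, and no decision rule in the documents says to read it so. Protocol 1.4 defines the optimal dose by several alternative criteria, none of them this slope.
- **Other output would help.** SAP 5.1.1 plans means and SDs by group and visit, in tables and graphs, and Protocol 10.5 lists mean change between and within arms. These could make a plateau visible, but neither supplies a 3000 v 2000 mg contrast with an interval.

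**Conclusion.** The concern holds as a gap in a secondary analysis. The coding rule is undefined and depends on the data. If the numeric branch is used, the slope cannot separate a gain at 2000 mg from one only at 3000 mg, with or without baseline as an outcome visit. If the factor branch is used, the step can be estimated, but the SAP does not name it: with treatment contrasts, the usual interaction coefficients compare each visit with the first one, not week 12 with week 8.

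The slope is still a sound test of any dose-response, and the primary week-12 comparison of DE with DS is untouched. The slope weights are exact for complete data. The percentages rest on the assumed effect range, because the endpoint SD is not given.

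**What to change.** Before unblinding, amend SAP 5.1.7:

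1. Drop the plateau rule and fix visit as a factor.
2. State whether baseline 31P-MRS is an outcome visit or a covariate. A covariate is optional: with complete data it does not affect the 3000 v 2000 mg contrast, but using one means lifting the bar on covariates.
3. Report, with 95% confidence intervals, the DE-DS contrast for 2000 v 1000 mg (week 8), for 3000 v 1000 mg (week 12), and their difference (3000 v 2000 mg).
4. Base any statement about 2000 against 3000 mg on that difference, and do not read a non-significant result as equality. A linear slope may stay as a labelled overall trend.

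This needs SAP wording and contrasts from a model already planned, with no new data. The drawback is the imprecision in step 5: the trial may have to report that the two doses cannot be separated.

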## 5.2 Methods for Continuous Secondary Endpoint

### 5.2.1 Descriptive Statistics

CSF NAD (or other metabolites of the NAD metabolome) measured by LC-MS will be summarized by group for visits V1 and V4 using descriptive statistics (N, mean, standard deviation). Descriptive

statistics will be based on non-imputed data. Data will be presented both in tabular and graphical format.

### 5.2.2 Primary Inferential Analysis

Analysis of covariance (ANCOVA) between the dose escalation (DE-group) and the dose stable group (DS-group), i.e. the regression of CSF NAD (or other metabolites of the NAD metabolome) at week 12 depending on randomization group and adjusted for CSF NAD (or other metabolites of the NAD metabolome) at baseline. No additional adjustments/covariates will be used. No correction for multiple testing will be performed.

The formula for this calculation in R is:

```
NAD_at_V4 ~ Group + NAD_at_V1
```

### 5.2.3 Effect Estimates

The primary effect estimate will be the B-coefficient with confidence intervals and Cohen's d. Cohen's d will be calculated as the difference in the means between two groups and divided by the pooled standard deviation.

The Beta coefficient will be calculated in R in the following manner:

```
Beta_coffecient = summary(lm_object)$coefficients
```

Confidence intervals will be calculated in R in the following manner:

```
Confidence_intervals = confint(lm_object)
```

P-values will be retrieved from the summary of the lm\_object:

```
P_values = summary(lm_object)$coefficients
```

### 5.2.4 Assumption Checks and Alternative Analyses

Assumptions for ANCOVA will be tested in the following manner:

Normal distribution of residuals: Normality of residuals will be assessed by QQ-plots and the Shapiro-Wilk test.

### 5.2.5 Missing Data

For the primary outcome, missing data occur if a patient has not completed the study or CSF collection has not been successful within the time window of the final visit 12 weeks  $\pm$  7 days.

As the primary analysis uses two timepoints (V1 and V4), in the case of a participant missing V4 measurements, this patient will not be included in the analysis.

### 5.2.6 Sensitivity Analyses

Sensitivity analysis will be performed by comparing the results of analysis with the FAS and PPS populations. If there is a notable difference this will be commented upon.

### 5.2.7 Secondary Analyses of the Secondary Endpoint

The *secondary analysis* of the *secondary endpoint* will be:

- Analysis of covariance (ANCOVA) between the dose stable (DS-group) and the placebo group (PL-group), i.e. the regression of CSF NAD (or other metabolites of the NAD metabolome)

at week 12 depending on randomization group and adjusted for CSF NAD (or other metabolites of the NAD metabolome) at baseline. No additional adjustments/covariates will be used. No correction for multiple testing will be performed.

The above mentioned analysis will be performed in the same manner as the primary analysis for the secondary outcome (see section 5.2.2).

### 5.3 Methods for Continuous Exploratory Endpoints

As described in section 4.4, due to the nature of the exploratory outcomes, the analysis method is subject to change. The preliminary plan is that they will be analysed in the same manner as the primary endpoint if they have observations at V1, V2, V3 and V4 (see sections 5.1.2 and 5.1.7) and the same manner as the secondary endpoint if they only have observations at V1 and V4 (see sections 5.2.2 and 5.2.7).

### 5.4 Additional Explorative Analyses

#### 5.4.1 Correlation analyses

Explorative correlation analyses comparing the following correlations with either Spearman or Pearson correlations are planned:

- Change in cerebral NAD levels measured by P-MRS vs NAD levels in CSF.
- Change in cerebral NAD levels measured by P-MRS vs NRRP expression.
- Change in cerebral NAD levels measured by P-MRS vs PDRP expression.
- Change in NAD levels in CSF vs NRRP expression.
- Change in NAD levels in CSF vs PDRP expression.
- Change in cerebral NAD levels measured by P-MRS vs the following clinical rating scales:
  - o MDS-UPDRS
  - o MDS-NMS
  - o MoCA
  - o mGIDS-PD
  - o EQ-5D-EL
- Change in NAD levels in CSF vs the following clinical rating scales:
  - o MDS-UPDRS
  - o MDS-NMS
  - o MoCA
  - o mGIDS-PD
  - o EQ-5D-EL
- Change in NRRP expression vs the following clinical rating scales:
  - o MDS-UPDRS
  - o MDS-NMS
  - o MoCA
  - o mGIDS-PD
  - o EQ-5D-EL
- Change in PDRP expression vs the following clinical rating scales:
  - o MDS-UPDRS
  - o MDS-NMS

- MoCA
- mGIDS-PD
- EQ-5D-EL
- Change in Blood NAD levels vs NAD levels in CSF
- Change in Blood NAD levels vs cerebral NAD levels measured by P-MRS
- Change in Blood NAD levels vs NRRP expression
- Change in Blood NAD levels vs PDRP expression

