**4) NR has a major impact on cerebral metabolism:** F-fluorodeoxyglucose positron emission tomography (FDG-PET), performed at baseline and 30 days of treatment, revealed that NR altered cerebral metabolic activity. The analysis revealed a significant ordinal trend pattern (i.e., metabolic network), which was represented by the first principal component (PC1), accounting for 20.6% of the variance in the paired data. This novel **NR-related metabolic pattern (NRRP)** was characterized by multiple regional metabolic changes, including bilateral metabolic reductions in the caudate and putamen, extending into the adjacent globus pallidus, and in the thalamus (**Fig 1D-E**). Interestingly, the NRRP overlapped spatially with the Parkinson's Disease-Related Pattern (PDRP), and changes in NRRP expression in the NR group resulted in partial normalization of the striatal and thalamic hypermetabolism (**Fig 1D**), typically

characterizing the PD brain. Furthermore, changes in NRRP expression in the NR group correlated significantly ( $r=-0.59$ ,  $p = 0.026$ ) with a decrease of the UPDRS ratings recorded at the time of PET (**Fig 1F**). These results indicate that NR ameliorates the cerebral metabolic pattern of PD, and this is associated with significant clinical improvement.

**5) NR has widespread metabolic and regulatory effects:** Metabolomics revealed highly significant increase in NAD-related metabolites in blood, muscle and CSF (**Fig 1G**), indicating that NR supplementation boosts NAD metabolism across tissues. Intriguingly, RNA-sequencing in blood and muscle biopsy showed a highly significant ( $FDR < 10^{-8}$ ) upregulation of the mitochondrial, proteasomal and lysosomal pathways in the NR group. These findings indicate that NR supplementation increases both mitochondrial respiration and proteostasis – two hallmark pathogenic processes involved in PD

[figure not shown]

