**KG2 – Confirm whether NR has a symptomatic clinical effect and assess its dose responsiveness.** The NADPARK and NR-SAFE studies showed that NR was associated with a clinical improvement, in the form of UPDRS decrease, and this correlated significantly with the increase in cerebral NAD levels and change in the brain metabolic network (NRRP). Furthermore, the clinical improvement was more pronounced with 3000 mg NR in the NR-SAFE study, compared to 1000 mg in the NADPARK study. These findings suggest that NR may be ameliorating neuronal function in PD, resulting in symptom improvement. Confirming this effect and assessing its dose-dependence will allow us to: **1)** determine the optimal clinical dose of NR in PD, and **2)** account for symptomatic effects in neuroprotection trials.

**KG3 – Determine the dose-dependence of the metabolic response to NR therapy.** The NADPARK study showed that a dose of 1000 mg NR daily augmented the NAD metabolome in PBMC, muscle and CSF. The NR-SAFE study suggested that a dose of 3000 mg NR daily leads to a more potent augmentation of the NAD metabolome in blood. The relationship between NR dose and metabolic response needs to be further explored in order to determine optimal dosing regimens.

**KG4 – Determine whether NR therapy enhance proteostasis in PD and characterize the dose dependence of this effect.** Impaired proteostasis plays a central role in PD and other neurodegenerative disorders, including Alzheimer's disease (AD) and amyotrophic lateral sclerosis (ALS). Our transcriptomic analyses in the NADPARK study indicated that NR therapy may enhance proteostasis by inducing the expression of both proteasomal and lysosomal pathways. If confirmed, this would suggest that NR targets

multiple major processes implicated in the pathophysiology of PD, including mitochondrial respiratory dysfunction, oxidative damage, lysosomal and proteasomal impairment, and neuroinflammation. Moreover, it is not known whether higher NR doses can induce stronger induction of proteostasis in PD.

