## N-DOSE Protocol v3.1

The analysis of exploratory endpoints will be performed in a similar manner as for the primary and secondary endpoints. ANCOVA will be used to compare endpoints at week 12, and LME will be used to compare change from baseline to week 4, week 8 and week 12.

In addition, for PET analyses, changes in network scores with treatment will be evaluated for each group separately using permutation tests. Relationships between network values, brain NAD levels and MDS-UPDRS motor ratings or between treatment-related changes in these variables will be evaluated using Pearson's product-moment correlations, whereas Spearman rank-order correlation coefficients will be computed for non-normally distributed variables.

Omics data will undergo rigorous quality control and filtering according to established best practice procedures, as we have previously described. The between visit change in this data will be assessed by a pairwise comparison between each NR group and the placebo group, using linear models with appropriate covariates as we have previously described. Comparison of adverse events and abnormal laboratory test results between the treatment and placebo groups will be analyzed descriptively.

Further details for the analysis are outlined in the statistical analysis plan (SAP) for the trial, and we refer the reader to this document.

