#### 2.3.2 Confidence Intervals and p-values

All calculated p-values will be two-sided and compared to a 5% significance level. If a p-value is less than 0.05, the corresponding treatment group difference will be denoted as statistically significant. All efficacy estimates will be presented with two-sided 95% confidence intervals. As there is only one primary null hypothesis to be tested in this trial, there will be no adjustments for multiplicity.

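### SAP 5.4.1 does not say how randomised arm enters its 29 exploratory correlations; if arms are pooled unadjusted, shared treatment effects can pass for individual-level association

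*SAP*

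**What the plan says.** SAP 5.4.1 introduces its list with "Explorative correlation analyses comparing the following correlations with either Spearman or Pearson correlations are planned". The list holds 5 pairs among the imaging and CSF measures, 4 × 5 pairs with the rating scales, and 4 pairs with blood NAD: 5 + 20 + 4 = 29. No arm term, stratification, analysis population or visit is given. The word for change stands before the first variable only, as in "Change in Blood NAD levels vs NRRP expression".

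Protocol 10.4 covers a subset: "Relationships between network values, brain NAD levels and MDS-UPDRS motor ratings or between treatment-related changes in these variables will be evaluated". It uses Pearson, or Spearman for variables that are not normally distributed, and also has no arm term. The preceding sentence does have a by-arm rule, "changes in network scores with treatment will be evaluated for each group separately using permutation tests", but that governs the permutation tests and not the correlations.

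SAP 2.3.2 applies a common threshold: "All calculated p-values will be two-sided and compared to a 5% significance level". It makes no multiplicity adjustment. SAP 5.4 labels the correlations as explorative.

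**The concern.** The three arms were chosen to differ in NAD change. If a second variable also responds to treatment, the arm means alone line the two up: placebo participants low on both, escalation participants high on both. A correlation over all participants then mixes the difference between arms with any association between individuals. Its p-value partly repeats the randomised comparison, while the natural interpretation is that people whose brain NAD rose more also changed more clinically.

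That interpretation matters to the sponsor. Protocol 1.4 (KG2) cites a correlation of clinical improvement with cerebral NAD and NRRP in earlier work when it suggests that NR may improve neuronal function. The NRRP–UPDRS result in Protocol 1.3.2 is described within the treated arm ("changes in NRRP expression in the NR group correlated significantly"). The present plan does not carry that restriction over.

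The silence also leaves the analyst to choose between pooled, within-arm and adjusted estimates after seeing the results.

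**Working it through.** **The plan's own figure.** There is none to reproduce. SAP 5.4.1 gives no N, power or error rate for the correlations.

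**Inputs**
- Arm sizes PL/DS/DE = 20/20/40 (Protocol 4.2), so weights are 0.25/0.25/0.5.
- Cerebral NAD change in percentage points: 0/27/81. The 27 is the factor 1.27 at 1000 mg, and 81 is three times that under the linear assumption (SAP 5.5). Placebo (−0.43%) is taken as 0.
- NAD SD: not given, so assumed. Protocol 1.3.2 reports paired P = 0.016. With n = 15, t = 2.739 on 14 df, so SD = 27 × √15 / 2.739 = 38. This supposes that the P value and the 27% come from the same data.
- MDS-UPDRS change: −1/−2.3/−14. The −1 and −14 are NR-SAFE placebo and 3000 mg (parts I–IV); the −2.3 is NADPARK at 1000 mg (parts I–III). These are different totals and different cohorts.
- UPDRS SD: √((13.7² + 12.7²)/2) = 13.2, from NR-SAFE, assumed for every arm.
- Within-arm correlation: zero in every arm, by construction.

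**Expected pooled correlation.** With zero within-arm correlation,

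ρ = B_xy / √[(σ_x² + B_xx)(σ_y² + B_yy)], where B_xy = Σ w_k(μ_xk − μ̄_x)(μ_yk − μ̄_y), and B_xx and B_yy are defined likewise.

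- μ̄_x = 0.25×27 + 0.5×81 = 47.25; μ̄_y = −(0.25×1 + 0.25×2.3 + 0.5×14) = −7.825.
- B_xy = 0.25(−47.25)(6.825) + 0.25(−20.25)(5.525) + 0.5(33.75)(−6.175) = −212.8.
- B_xx = 1230.2; B_yy = 38.3.
- ρ = −212.8 / √[(1444 + 1230.2)(174.2 + 38.3)] = −0.28.

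With N = 80, p < 0.05 needs |r| > 1.991/√(78 + 1.991²) = 0.22, so the expected value alone exceeds the threshold.

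**Simulated rejection rates** (normal data, no dropout, two-sided 5%, Pearson; Spearman is nearly the same)

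| NAD change PL/DS/DE | UPDRS change | Expected r | Pooled | Arm-adjusted |
|---|---|---|---|---|
| 0/27/81 (linear) | −1/−2.3/−14 | −0.28 | about 75% | 5% |
| 0/27/54 (weaker dose response) | same | −0.20 | about 45% | 5% |
| 0/27/81 | halved | −0.15 | 27% | 5% |
| 0/27/27 (plateau) | same | −0.08 | 11% | 5% |
| 0/27/27 | halved | −0.04 | 7% | 5% |
| 0/27/81 | no effect | 0 | 5% | 5% |

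The adjusted test removes arm means from both variables and uses N − 4 = 76 df instead of 78.

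**Sensitivity.** With a linear UPDRS dose response instead of the mixed means (NAD 0.71 and 2.12 SD, UPDRS 0.33 and 0.98 SD above placebo), the pooled rate is 68%. In general terms, with linear effects of equal size on both variables (DE versus placebo), it is 7% at 0.5 SD, 29% at 1 SD, 80% at 1.5 SD and 99% at 2 SD.

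**Visit.** CSF is taken only at baseline and week 12 (Protocol 6.1), which fixes the interval for the 9 pairs that include CSF. The other 20 could use week 4, 8 or 12. At week 4 both NR arms are on the same dose, so the arm structure differs by visit.

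**The case against.** The strongest reply is that pooling is assumed. The artefact arises only if arms are combined without adjustment, and the text neither states nor excludes that. The sponsor's own NRRP–UPDRS precedent is within the NR group, and a within-arm analysis would be free of it. This stands as a limit: a reader might infer that the plan prescribes pooled correlations, and it does not. Pooling is only the natural reading of an instruction that names a coefficient and no grouping, beside a sentence that does specify grouping for another test.

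A reader might also infer that all 29 pairs are affected. The documents do not support that. Both variables must respond to treatment, and the protocol and SAP quote no effects for MDS-NMS, MoCA, mGIDS-PD or EQ-5D, which make up 4 × 4 = 16 of the pairs.

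The 75% figure uses favourable inputs: the linear NAD assumption, a back-derived SD, and UPDRS means joined across two small trials. A NAD plateau is one form of the primary null hypothesis, and it brings the rate down to 11%.

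Next, a pooled correlation is not strictly a false positive when dose moves both variables. Association across doses is a fair descriptive target in a dose trial. That is correct, and the error would lie in reading it as an individual-level link. Showing the pooled value with a descriptive label meets this objection.

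Finally, KG2 concerns earlier trials and is worded cautiously. Neither document ties a claim or decision to the correlations in SAP 5.4.1.

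**Conclusion.** The point holds as an omission with a foreseeable consequence. SAP 5.4.1 leaves arm handling, visit and the form of the second variable open. If the method is run as plain correlations on all participants, shared treatment effects inflate the correlations. For cerebral NAD against MDS-UPDRS with no within-arm association, the chance of p < 0.05 runs from about 75% under the plan's linear NAD assumption to 11% under a plateau, and to 7% with the UPDRS effect also halved. It is nominal when only one variable responds. Adjustment for arm brings it to about 5% in every case.

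The sizes rest on the assumed NAD SD of 38 points, the mixed UPDRS inputs, normality, equal SDs and no dropout. The mechanism does not depend on those particular values, but it does need treatment effects on both variables.

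It would go too far to conclude that the planned correlations must be significant, or that the trial's efficacy conclusions are at risk. The analyses are explorative, and the primary and secondary endpoint comparisons do not use them. Severity: minor.

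**What to change.** Add to SAP 5.4.1 that each correlation is between the change in one variable and the change in the other at the same named visit, estimated as a partial correlation adjusted for randomised group. An equivalent test is a regression of one change on the other with group as a factor. For Spearman, rank both variables first and then adjust the ranks for group; in the scenarios above this also held the rate at about 5%. State which participants are included. Show within-arm estimates beside the adjusted one, and label any unadjusted pooled value as descriptive.

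The adjusted estimate should lead. With 20 in an arm, significance needs |r| > 2.101/√(18 + 2.101²) = 0.44, so the separate estimates for the placebo and dose-stable arms will be imprecise.

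The cost is a short addition to the SAP, one model term and about two degrees of freedom. Trial conduct does not change. If the choice is made after unblinding, the report should say so.
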